10.2 Investigator Reports

Investigators are required to prepare and submit to BIOTRONIK, Inc. the following complete, accurate and timely reports on this study, when necessary:

- Notification of a subject death during the study
- Any unanticipated adverse device effects
- Notification of the withdrawal of IRB approval
- Annual progress reports prepared for the IRB

- Notification that informed consent was not obtained from a subject
- Final summary report prepared for the IRB
- Any other information upon the request of an IRB, regulatory authority, or BIOTRONIK, Inc.

Table 9 outlines the responsibilities, including time constraints, for submitting the above reports.

Table 9: Investigator Reports

Type of Report	Prepared by Investigator for:	Time Constraints of Notification
Subject death during study	BIOTRONIK, Inc., IRB	As soon as possible and as required by reviewing IRB
Unanticipated adverse device effect	BIOTRONIK, Inc., IRB	Within 10 working days after notification of effect
Serious or life-threatening unanticipated adverse device effect	BIOTRONIK, Inc., IRB	Within 2 working days after notification of effect
Subject withdrawal	BIOTRONIK, Inc.	Within 5 working days after notification of withdrawal
Withdrawal of IRB approval	BIOTRONIK, Inc.	Within 5 working days of receipt of notice of withdrawal of approval
Progress report(s)	BIOTRONIK, Inc., IRB	Submitted no less than yearly
Significant deviations from study plan	BIOTRONIK, Inc., IRB	Within 5 working days after emergency to protect life or physical well-being of subject, otherwise prior approval by BIOTRONIK, Inc. is required
Informed consent not obtained	BIOTRONIK, Inc., IRB	Within 5 working days of occurrence
Final summary report	BIOTRONIK, Inc., IRB	Within 3 months after completion or termination of the study

10.3 Sponsor Records and Reports

BIOTRONIK, Inc. will maintain the following records:

- All correspondence with the investigator(s), IRBs, and FDA that pertains to the study
- Investigational device shipment and inventory reconciliation reports
- Investigator agreements, financial disclosures, and current curriculum vitae
- Name and address of each investigator and each IRB that is involved with the investigation
- Adverse events and complaints

- Adverse device effects (whether anticipated or unanticipated)
- Electronic Case Report Form data
- Confirmation of completed subject informed consent forms
- Clinical investigation protocol and report of prior investigations
- Screening visit reports
- Monitoring reports
- Clinical progress reports
- Statement of the extent to which the good manufacturing practice regulation in part 21 CFR 820 will be followed in manufacturing the device

BIOTRONIK, Inc. is responsible for preparing the following reports, when necessary:

Table 10: Sponsor Reporting Responsibilities

Type of Report	Prepared by BIOTRONIK for	Time Constraints of Notification
Unanticipated adverse device effect	FDA, all reviewing IRBs, participating investigators	Within 10 working days after notification of effect
Withdrawal of IRB approval	FDA, all reviewing IRBs, participating investigators	Within 5 working days of receipt of notice of withdrawal of approval
Withdrawal of FDA approval	Reviewing IRBs, participating investigators	Within 5 working days
Current investigator list	FDA	Names and addresses of participating investigators at 6 month intervals
Progress report	FDA, all reviewing IRBs	Submitted at least annually
Recall and disposition	FDA, all reviewing IRBs	Within 30 working days and will include reasons for any request that an investigator return, repair, or otherwise dispose of any investigational leads
Final report	FDA, all reviewing IRBs, participating investigators	Notification within 30 working days of the completion or termination of the investigation. A final report will be submitted within 6 months after completion or termination of the study.
Informed consent not obtained	FDA	Within 5 working days of notification of occurrence

11. MULTIPOLE PACING SUB-STUDY

11.1 Introduction

This QP ExCELS clinical sub-study is an FDA required post-approval study for the US market released BIOTRONIK MultiPole Pacing (MPP) feature (PMA P050023/S107) of the Ilivia HF-T QP family CRT-D system (PMA P050023/S103).

11.1.1 Sub-Study Overview

Since the initial PMA approvals of Cardiac Resynchronization Therapy (CRT) devices, features have evolved to provide additional programmability designed to maximize patient benefit. Despite the proven benefit of CRT in the indicated population, up to one-third of patients do not respond to the therapy.¹

In the field of CRT, the adaption of the IS4 connector standard was the most prominent improvement within the recent past. This IS4 connector allows the usage of left ventricular (LV) leads that offer four separate poles which results in an increased number of effectively different pacing polarities. Along with the quadripolar (QP) LV lead comes the possibility of stimulating more than one LV pacing site within one cardiac cycle.

Studies have shown that multiple point LV pacing via a QP LV lead may be an alternative approach to improve CRT response by delivering multiple LV pacing pulses, simultaneously recruiting a larger volume of myocardium.² A recent IDE study from St. Jude Medical showed that quadripolar multiple point LV pacing (MultiPoint™ Pacing algorithm) was non-inferior to standard quadripolar biventricular pacing.³

QP ExCELS is a prospective, non-randomized, multi-center clinical investigation designed to satisfy U.S. Food and Drug Administration (FDA) requirements for pre-market submission of the Sentus OTW QP LV leads. The QP ExCELS study enrolls subjects with a standard CRT-D indication prior to implantation with a BIOTRONIK Sentus QP LV lead and US a market released BIOTRONIK CRT-D with an IS4 port for the LV lead.

11.1.2 MultiPole Pacing (MPP) Description

[figure not shown]
The US market released MultiPole Pacing feature of the Ilivia HF-T QP family CRT-D systems allows left ventricular pacing in two different vectors within a single cardiac cycle using the same quadripolar lead in order to improve synchronization of the contraction pattern. Both left ventricular stimuli will either be before the right ventricular pace (1st LV – 2nd LV - RV) or after the right ventricular pace (RV-1st LV – 2nd LV). The second LV stimulus will only be capable of delivering the second pacing stimulus in the left ventricle; sensing and timing will not be affected by 2nd LV. The delay between the two left ventricular paces is programmable between 0 ms and 50 ms in 5 ms steps. All 12 currently approved pacing configurations are available for both pacing stimuli. However, the same pacing vector cannot be used for both stimuli. Pacing output and interventricular delays can be programmed independently. There is no change to the same parameter ranges available for pacing amplitude and pulse width (0.5 to 7.5 V and 0.4 to 1.5 ms, respectively). The programmable parameters for the MultiPole Pacing feature are listed in 11.

Table 11: Programmable Parameters for MultiPole Pacing

Parameter	Programmable range
LV MultiPole stimulation	OFF, 1st LV-2nd LV-RV, RV-1st LV-2nd LV
LV stimulation amplitude (1st LV and 2nd LV)	0.5 to 7.5 V
LV stimulation width (1st LV and 2nd LV)	0.4 to 1.5 ms
Interval 1st LV – 2nd LV	0 to 50 ms
Stimulation configuration (1st LV and 2nd LV)	LV1 Tip → LV2 Ring LV1 Tip → LV4 Ring LV1 Tip → RV Coil LV1 Tip → ICD LV2 Ring → LV1 Tip LV2 Ring → LV4 Ring LV2 Ring → RV Coil LV3 Ring → LV2 Ring LV3 Ring → LV4 Ring LV3 Ring → RV Coil LV4 Ring → LV2 Ring LV4 Ring → RV Coil

MultiPole Pacing is programmable using programmer software that can be used with one of BIOTRONIK’s programmers, either the ICS 3000 (P950037/S035, dated May 18, 2005) or the Renamic (P950037/S089, dated April 15, 2011). The user accesses the feature from the Bradycardia/CRT parameters tab (Figure 9).

Figure 9: Programming MultiPole Pacing

As shown in Figure 9 and Figure 10 the polarity, pulse amplitude, and pulse width for the two LV stimuli can be programmed independently.

Figure 10: Programming 1st LV Stimulus

[figure not shown]

Figure 11: Programming 2nd LV Stimulus

[figure not shown]

Figure 11 and Figure 12 compare the timing of the ventricular stimuli depending on which chamber is selected to be initially paced. When the right ventricle is paced first, the LV-LV delay starts after the V-V delay, whereas the V-V and LV-LV delays start simultaneously when the left ventricle is paced first.

Figure 12: V-V Delay, LV First

[figure not shown]
[figure not shown]

Figure 13: V-V Delay, RV First

11.1.3 Published Results for Multipoint LV Pacing

Forleo et. al, 2016 evaluated the experience of the St. Jude Medical MPP-capable CRT-D devices (Unify Quadra MP or Quadra Assura MP) connected to a quadripolar LV lead (Quartet™). A total of 507 patients in whom these devices had been successfully implanted were enrolled between August 2013 and May 2015. The analyses included: (i) current clinical practices for the management of such patients, and (ii) the impact of MPP on heart failure clinical composite response and on the absolute change in ejection fraction (EF) at 6 months. Multipoint pacing was programmed to 'ON' in 46% of patients before discharge. Methods of optimizing MPP programming were most commonly based on either the greatest narrowing of the QRS complex (38%) or the electrical delays between the electrodes (34%). Clinical and echocardiographic follow-up data were evaluated in 232 patients whom data were available both at the baseline and the 6-month follow-up examination. These patients were divided into two groups according to whether MPP was programmed to 'ON' (n = 94) or 'OFF' (n = 138) at the time of discharge. At 6 months, EF was significantly higher in the MPP group than in the biventricular-pacing group (39.1 ± 9.6 vs. 34.7 ± 7.6%; P < 0.001). Even after adjustments, early MPP activation remained an independent predictor of absolute increase in LVEF of ≥5% (odds ratio 2.5; P = 0.001). At 6 months, an improvement in clinical composite score was recorded in a greater proportion of patients with MPP-ON than in controls (56 vs. 38%; P = 0.009). On comparing optimal MPP and conventional vectors, QRS was also seen to have decreased significantly (P < 0.001).²

The recent MultiPoint™ Pacing (MPP) IDE Study from St. Jude Medical showed that quadripolar multiple point LV pacing (MultiPoint™ Pacing algorithm) was non-inferior to standard quadripolar biventricular pacing. The multicenter study enrolled and followed 506 subjects with a standard CRT-D indication who were implanted with a CRT-D system (Quartet™ LV lead with a Quadra CRT-D) capable of delivering either quadripolar biventricular pacing or MPP. Quadripolar Bi-V pacing was activated at implant. At 3 months post-implant, patients' responder status was assessed, both responders and non-responders were randomized, and 1:1 randomization (Bi-V or MPP) was stratified by responder status. The primary efficacy endpoint (freedom from system-related complications through 9 months) was 93.2%, (97.5% lower confidence bound 90.4%) was greater than the objective performance criterion of 75%. The primary efficacy endpoint was met for both intention-to-treat and as-treated populations in 381 randomized patients (ITT, $p=0.013$ and as-treated, $p=0.008$, respectively). For patients in the MPP arm programmed with wide cathode spacing and the shortest intraventricular timing delay (5ms), MPP provided significantly higher clinical responder rate (between 3 and 9 months) up to 87% ($p=0.003$ vs $<30\text{mm}$) and converted 100% non-responders to responders ($p=0.006$ vs $<30\text{mm}$).³

11.2 Sub-Study Design

The objective of this MultiPole Pacing sub-study is to demonstrate that the MPP feature is effective by converting a percentage of CRT non-responders to responders. Each subject's responder status will be assessed using a Clinical Composite Score (CCS)⁴ including three components: NYHA Class, heart failure (HF) hospitalizations, and cardiovascular death.

The MPP sub-study is a single-arm, multi-center, prospective trial within the ongoing QP ExCELS study. Eligible patients will have been enrolled in QP ExCELS and successfully implanted with the BIOTRONIK Ilivia HF-T QP family CRT-D system, or future-marketed CRT-D system with the MPP feature, and have received standard biventricular (BiV) pacing (i.e. without MPP) prior to a 6-Month CCS assessment or at the time of the QP ExCELS 3-month follow-up with a HF hospitalization event.

Visit intervals below are specified according to time since implant to minimize confusion between the differing enrollment timing into the QP ExCELS study and MPP sub-study.

At the QP ExCELS 6-month Follow-up, a CCS assessment will be completed for all QP ExCELS enrolled subjects who are currently receiving BiV pacing, including NYHA class and HF hospitalization status. Additionally, a Patient Global Assessment (PGA) will be collected. A responder status will be derived classifying these subjects as "Improved", "Worsened", or "Unchanged" using the following definitions:

CRT Responder Classification at QP ExCELS 6-Month Follow-up (evaluated compared to QP ExCELS Enrollment Visit)*:

- “Improved”:
 - No HF hospitalization has occurred, AND
 - NYHA class is improved
- “Unchanged”:
 - No HF hospitalization has occurred, AND
 - NYHA class is unchanged
- “Worsened”:
 - HF hospitalization has occurred, OR
 - NYHA class is worsened

Classification of prior “HF hospitalization” event at the time of MPP screening/enrollment and NYHA class will be determined and reported by the investigator.

Those subjects responder classification determined to be “Worsened” or “Unchanged” may be approached for enrollment into the MPP sub-study. These subjects must sign a separate MPP sub-study Informed Consent prior to enrollment. Those that decline enrolling into the MPP sub-study will continue to be followed according to the primary QP ExCELS protocol.

After enrollment into the MPP sub-study, the MPP feature will be programmed ON and an MPP optimization procedure may be performed for all subjects according to the site’s optimization method (see Section 11.3.3.1).

At a 9-Month Follow-up[†] (90 ± 30 days post-MPP enrollment), each subject will repeat the NYHA classification, PGA, and HF hospitalization status, in addition to the standard QP ExCELS required lead testing.

At a 12-Month Follow-up[†] (180 ± 30 days post-MPP enrollment), each subject will repeat the NYHA classification, PGA, and HF hospitalization status. Following the 12-Month Follow-up, all subjects may be programmed to MPP or standard BiV pacing, per physician discretion.

Subjects enrolled in the MPP sub-study will rejoin the main QP ExCELS study at the 12-Month Follow-up[†]; however, no further CCS will be assessed.

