1. INTRODUCTION

This clinical study protocol includes a pre-market study phase and an FDA required post-approval registry phase for BIOTRONIK's Sentus QP lead. During the study safety and effectiveness data will be collected and evaluated for the Sentus QP lead. The pre-market phase will enroll up to 314 subjects at up to 125 clinical study sites worldwide for pre-market analyses. Up to 75 study sites are planned within the United States. U.S. sites will enroll up to 1,754 subjects as part of a post-approval study. This clinical protocol additionally includes an FDA required post-approval MultiPole Pacing (MPP) sub-study to demonstrate the MPP feature can effectively convert a percentage of CRT non-responders to responders.

Subjects eligible for the study are receiving a new (*de novo*) implant or undergoing an upgrade from an existing ICD or pacemaker implant with no prior attempt at LV lead placement. Prior to enrollment, eligible subjects will be identified and will provide written informed consent. Post implant, subjects will be seen for a pre-hospital discharge or wound check evaluation plus in-office follow-ups at 3, 6, and 12 months. Thereafter, subjects enrolled in U.S. sites will continue to have follow-up visits every 6 months until 5 years post-implant.

Within the U.S., the Sentus QP LV leads are considered investigational devices. All other devices utilized in conjunction with this study are U.S. market approved and prescribed by physicians according to approved indications for use.

This clinical study protocol is a U.S. specific amendment for the QP ExCELS study and is only for U.S. study sites. The study sponsor for all U.S. sites is BIOTRONIK, Inc., Lake Oswego, OR, USA. Enrollment at non-U.S sites has ended with the last subject enrolled on February 29, 2016. It is anticipated that the Sentus QP LV lead will receive FDA approval during the course of the trial. BIOTRONIK will notify all sites when FDA approval is granted. The non-US subjects were enrolled and followed for the pre-market cohort only. These subjects end their study participation at the 12-month follow-up. The sponsor for all non-U.S. sites is BIOTRONIK SE & Co. KG, Berlin, Germany.

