11.2.1 Study Endpoints

This sub-study includes the assessment of one primary effectiveness endpoint, as well as three secondary endpoints. The hypothesis associated with the primary endpoint is in a superiority format.

* Subjects may be enrolled in the MPP sub-study at the 3-Month QP ExCELS follow-up if the subject received continuous standard biventricular (BiV) pacing from implant to the 3-Month follow-up with a HF hospitalization event and will be followed for 6 months in the MPP sub-study with MPP sub-study data collected at a 6-month follow-up and 9-month follow-up.

11.2.1.1 Primary Endpoint 1

The purpose of primary endpoint 1 is to evaluate the CRT responder status with the MPP feature within the Ilivia 7 HF-T QP family CRT-D, or future-marketed CRT-D system, compared to a pre-specified performance goal.

The associated hypothesis is evaluated based on a CCS determining a responder classification based on changes in NYHA class, HF hospitalization, and cardiovascular death.

A responder status will be derived classifying these subjects as “Improved”, “Worsened”, or “Unchanged” using the following definitions:

Responder Classification at 12-Month Follow-up (evaluated compared to MPP Enrollment Visit occurring at 6 months)[†]:

- “Improved”:
 - No HF hospitalization or cardiovascular death, AND
 - NYHA class is improved
- “Unchanged”:
 - No HF hospitalization or cardiovascular death, AND
 - NYHA class is unchanged
- “Worsened”:
 - HF hospitalization or cardiovascular death has occurred, OR
 - NYHA class is worsened

Ho: The proportion of subjects (P) who are classified as “Improved” is not superior to a performance goal (PG) of 3%.

$$PG \geq P$$

Ha: The proportion of subjects who are classified as “Improved” is superior to a performance goal of 3%.

$$PG < P$$

A rejection of the null hypothesis would indicate that the proportion of subjects classified as “Improved” is superior to 3%.

11.2.1.2 Secondary Endpoint 1- Freedom from MPP system related adverse events requiring additional invasive intervention to resolve at 6 months

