The purpose of Secondary Endpoint 1 is to evaluate adverse events that require additional invasive intervention to resolve, specifically related to the MPP feature of the Ilivia HF-T QP family, or future-marketed CRT-D system with the MPP feature. These adverse events include any software issues related to MPP programming or any adverse event that occurs while MPP is enabled and that may be attributed to the use of the MPP feature.

[†] Evaluated at 9-month follow-up if MPP sub-study enrollment visit occurred at 3 months.

11.2.1.3 Secondary Endpoint 2 - Evaluate CCS + PGA Responder Status utilizing a modified CCS that incorporates the Patient Global Assessment

The purpose of Secondary Endpoint 2 is to evaluate a modified CCS, determining a responder classification based on changes in NYHA class, Patient Global Assessment (PGA), HF hospitalization, and cardiovascular death, where the PGA will ask subjects to assess how their overall status has changed since prior to receiving CRT therapy (markedly better, better, unchanged, worse, markedly worse).

Modified Responder Classification (CCS + PGA) at 12-Month Follow-up[‡]:

- “Improved”:
 - No HF hospitalization or cardiovascular death, AND
 - Neither NYHA class is worsened or PGA is worsened (“worse” or “markedly worse”), AND
 - NYHA class is improved or PGA is improved (“better” or “markedly better”)
- “Unchanged”:
 - No HF hospitalization or cardiovascular death, AND
 - NYHA class is unchanged, AND
 - PGA is unchanged (“unchanged”)
- “Worsened”:
 - HF hospitalization or cardiovascular death has occurred, OR
 - NYHA class is worsened or PGA is worsened (“worse” or “markedly worse”)

11.2.1.4 Secondary Endpoint 3: Evaluate CCS Responder Status utilizing a modified Responder Classification

The purpose of Secondary Endpoint 3 is to evaluate a modified Responder Classification in which both “Improved” and “Unchanged” subjects will be classified as responders. At the time of enrollment into the MPP sub-study, MPP sub-study subjects have already been found to have no change or worsening in their HF status with BiV pacing. Since HF is a chronic and progressive condition, these subjects may be expected to continue to worsen during the MPP follow-up period or remain stable with careful management. In this secondary endpoint, a status of “Unchanged” (in addition to “Improved”) during the MPP follow-up period will be considered a responder to MPP.

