11.2.1.5 Additional Data of Interest

Additional information will be collected to characterize the study population, implanted system, and progress of the clinical investigation. The data will be statistically analyzed, where appropriate. Further data of interest will include:

- Patient Global Assessment (PGA) at each visit
- MPP programmed settings
- Adverse events attributed to MPP feature
- Device initial and final programmed settings
- Methods utilized to optimize MPP, AV and/or V-V timing

11.2.2 **Study Size and Duration**

The MPP sub-study will enroll up to 100 subjects at up to 75 sites within the United States who are participating in the QP ExCELS study. Subjects in the MPP sub-study will be followed for 6 months (180 ± 30 days post-MPP enrollment). Subjects enrolled in the MPP sub-study will rejoin the main QP ExCELS study after completion of their 12-month MPP follow-up[§].

11.2.3 **Sample-Size Analysis**

The investigation is designed to limit the number of patients involved while still exposing the device to a sufficiently large patient population in order to ensure a representative and statistically meaningful sample.

Primary Endpoint 1 Sample Size

The estimated sample size requirements are based on a superiority comparison of the proportion of responders to a performance goal of 3%, chosen based on the assumption that any conversion of non-responders to responders is clinically relevant. A performance goal of 3% was chosen rather than 0% to account for variability (“noise”) around 0%, for example, due to infrequent subjects who are late responders to CRT or improve regardless of MPP. The expected result is estimated at a 10% conversion of non-responders to responders.

There is limited published data available for mid- to long-term follow-up CRT response with multiple point LV pacing in any population. Additionally, no published data could be found related to CRT response with multiple point LV pacing in an “all-comer non-responder” population. The St. Jude Medical MultiPoint Pacing IDE Study^{3,5} (“St. Jude IDE study”, NCT01786993) evaluated CRT response based on a Clinical Composite Score (CCS) after 3 months of BiV pacing. Subjects were then randomized to the MultiPoint™ Pacing treatment arm

[§] If an MPP sub-study subject was enrolled at the 3-Month QP ExCELS follow-up, they will re-join the main QP ExCELS study after completion of their 9-month MPP follow-up.

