11.2.4 Data Analyses

Classification of "HF hospitalization" and "cardiovascular death" events for use in primary endpoint 1, secondary endpoint 2, and secondary endpoint 3 analyses will be determined by a Clinical Events Committee (Section 11.3.4).

Descriptive statistics will be used to present and summarize the data collected in the clinical study. Frequency distributions and cross tabulations will be presented for discrete variables. Means, standard errors, and ranges will be presented for continuous variables.

For primary endpoint 1, the lower, one-sided, exact 97.5% bound for the observed proportion of responders ("improved") would have to exceed 3% for rejection of the null hypothesis.

Additional related analyses to be performed for the endpoint include:

- Descriptive statistics for observed changes in NYHA class and frequency tabulations for the other components of the Clinical Composite Score.

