11.3.4 Clinical Events Committee – MPP Sub-Study Events

The QP ExCELS Clinical Events Committee (CEC) described in Section 5.1 will adjudicate all adverse events that require additional invasive intervention to resolve which may be related to the MPP feature. These events include any software issues related to MPP programming or any adverse event that occurs while MPP is enabled and that may be attributed to the use of the MPP feature. The CEC will

^{††} Subjects enrolled at the 3-Month follow-up due to a prior HF hospitalization event will be followed at 6-months (90 ± 30 days post-MPP enrollment).

^{‡‡} Subjects enrolled at the 3-Month follow-up due to a prior HF hospitalization event will be seen at 9-months (180 ± 30 days post-MPP enrollment) and join the main QP ExCELS study at the 12-Month visit.

indicate whether the adverse event is related, possibly related, not related, or has an unknown relation to the MPP feature.

In addition, the CEC will adjudicate all deaths reported while participating in the MPP sub-study and classify each death as cardiovascular, vascular, non-cardiovascular/vascular, or unknown.

The CEC will adjudicate all reported protocol-defined hospitalizations while a subject is enrolled in the MPP sub-study. Hospitalization events will be classified as cardiovascular, vascular, non-cardiovascular/vascular, or unknown. Additionally, hospitalizations classified as cardiovascular will be further classified as a HF hospitalization, non-HF hospitalization, or unknown. Hospitalization events reported by the investigator as part of the initial responder classification for enrollment into the MPP sub-study will not be adjudicated by the CEC.

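### Does the MPP sub-study's objective promise more than a single-arm test against 3% can show?

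*Combined protocol and SAP*

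**What the plan says.** Section 11.2 describes a single-arm sub-study whose objective is to "demonstrate that the MPP feature is effective by converting a percentage of CRT non-responders to responders". Section 1 says its purpose is to "demonstrate the MPP feature can effectively convert a percentage of CRT non-responders to responders".

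Other sections are more restrained:

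- The synopsis describes the primary endpoint only as an evaluation of responder status with the feature.
- Section 11.2.1.1 compares the proportion Improved with a performance goal of 3%. It states what a positive result means: "A rejection of the null hypothesis would indicate that the proportion of subjects classified as" Improved is superior to 3%.
- Section 11.2.4 sets the decision rule: "the lower, one-sided, exact 97.5% bound for the observed proportion of responders" must exceed 3%.
- Section 11.2.3 explains that the goal is 3% and not 0% to allow for noise, for example "due to infrequent subjects who are late responders to CRT or improve regardless of MPP". It gives no rate or source for that background.
- Section 11.2.1.4 says of the same population that "these subjects may be expected to continue to worsen during the MPP follow-up period or remain stable with careful management".
- Section 11.4.2 says that no current data support superiority over conventional biventricular (BiV) pacing, and that conversion of non-responders is unproven.

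Improved requires a better NYHA class than at MPP enrollment, with no heart failure hospitalization or cardiovascular death. The investigator rates NYHA (Section 11.3.2.1). The Clinical Events Committee (CEC) classifies the events; Section 11.3.4 says "The CEC will adjudicate all reported protocol-defined hospitalizations while a subject is enrolled in the MPP sub-study".

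**The concern.** Converting non-responders is a causal claim, and one arm compared with a fixed number does not separate a pacing effect from its rivals. There are three such rivals:

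- **Late response.** Some subjects may respond late to the BiV pacing they have already had.
- **Fluctuation in NYHA class.** Most subjects enter because their status was Unchanged or Worsened, and change is then measured from that visit. A subject whose class worsened and later returned to its pre-implant level counts as Improved. This does not apply to those who enter on a heart failure hospitalization alone.
- **Unblinded rating.** The investigator who rates NYHA knows that MPP is on.

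The 3% goal carries the whole allowance for these, and its rationale is verbal only. If the true background were a point or two higher, a pass would be weaker evidence for MPP than the nominal 2.5% error rate suggests. At stake is whether a positive result of this FDA-required study could be read as proof that MPP converts non-responders.

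**Working it through.** **Inputs.** Goal p0 = 3%, expected rate p1 = 10%, one-sided alpha 0.025, power 80%, n = 90 evaluable (Section 11.2.3); exact lower bound as the decision rule (Section 11.2.4); 10% loss to follow-up (Section 11.2.4.1).

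**Step 1: reproduce the plan's figure.** The exact lower bound L for r Improved out of n solves P(Bin(n, L) ≥ r) = 0.025.

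- r = 6, n = 90: L = 2.49%, which fails.
- r = 7, n = 90: L = 3.18%, which passes.

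The pass mark is therefore 7/90 = 7.8%.

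- Type I error: P(Bin(90, 0.03) ≥ 7) = 0.0188, below 0.025.
- Power: P(Bin(90, 0.10) ≥ 7) = 0.8075. At n = 89 it is 0.7983, so 90 is the smallest n reaching 80%.
- Enrollment: 90/0.9 = 100.

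The stated 90 and 100 are correct, and error against the stated null is controlled.

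**Step 2: what a pass says about MPP.** Suppose MPP has no effect and a fraction b would be classified Improved anyway. The chance of passing is P(Bin(90, b) ≥ 7):

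| Assumed background b | Chance of passing, n = 90 |
|---|---|
| 2% | 0.2% |
| 3% | 1.9% |
| 4% | 6.9% |
| 5% | 16.4% |

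The chance stays at or below 2.5% while b is 3.18% or less; by construction this is the lower bound for 7/90. Every row other than 3% is an assumption, since the documents give no background rate. If all 100 enrolled were evaluable, the pass mark would be 8 and the chances at 3%, 4% and 5% would be 1.1%, 4.8% and 12.8%.

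**Step 3: what a control arm would cost, for scale.** To compare 10% with an assumed 3% (two-sided 0.05, 80% power, mean rate 0.065):

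n per arm = [1.96·√(2·0.065·0.935) + 0.842·√(0.03·0.97 + 0.10·0.90)]² / 0.07² ≈ 194.

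That is 2 × 194 = 388 evaluable subjects, against 90 now.

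**Step 4: compare objective and hypothesis.** The objective sentences in Sections 1 and 11.2 speak of converting non-responders. Section 11.2.1.1, which governs the analysis, speaks only of a proportion above 3%. The step from one to the other is the Section 11.2.3 assumption that about 3% covers improvement without MPP. The link is stated but not quantified.

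**The case for a change.** The strongest case for a change is that the plan announces a conclusion its design cannot deliver alone. The allowance for background improvement has no data behind it, and Section 11.2.3 itself says the published MPP studies are not directly applicable, so they supply no rate. The inference is also sensitive: moving the background from 3% to 5% raises the chance of a pass without any MPP effect from 1.9% to 16.4%. Aligning two sentences with Section 11.2.1.1, or adding a caveat, would cost almost nothing.

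Part of this stands. The two sentences do say more than the test shows, and attribution to MPP does rest on an unquantified assumption. But the documents do not show that 3% is too low. Their only indications, that such subjects are infrequent and that the population is expected to worsen or stay stable, point to a low rate. The single-arm design is stated openly, the permitted conclusion is already correct, and the risk section says conversion is unproven. The unblinded-rating worry concerns NYHA only, because the CEC classifies the hospitalizations and deaths.

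A side issue is that Table 6 marks NYHA at enrollment only, while Section 11.3.2.1 calls for it at all protocol-defined follow-ups. In context that sentence most naturally means the sub-study visits. For the 6-month value, Section 3.4.5 sends sites to Section 11, where Section 11.2 requires it. At most this is clerical. A descriptive comparison with non-responders left on BiV pacing would need a 12-month NYHA that the main-study schedule does not list.

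**Conclusion.** The wording of the objective is looser than the hypothesis, but no change to the plan is needed. The test, the 3% goal and the 90/100 sample size are internally correct: the error rate is 1.9% at the goal and power is 80.75% at 10%. The conclusion the plan allows is the one the test supports. Reading a pass as an MPP effect at the nominal error rate requires a background of no more than 3.18% at n = 90. The plan discloses that kind of allowance without quantifying it, and nothing in the documents contradicts it.

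Rewording Sections 1 and 11.2 would leave every analysis and decision as it is, so there is no gain beyond tidier prose. The single-arm design is a fair trade-off given the roughly 388 evaluable subjects a controlled comparison would need under the same assumed rates. Analysts who follow Section 11.2.1.1 will report a proportion with its exact bound against 3%, and can note the absence of a control when interpreting it. This verdict rests on the documents alone; a sourced background rate clearly above 3% would reopen the question of the goal itself.
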